STUDY PROTOCOL DOCUMENT

Document Title:

Detailed Description of Study Procedures and Statistical Analysis

Document Update Date:

14 January 2026

Prepared for:

ClinicalTrials.gov Registration

Detailed Description

This study was conducted with individuals who agreed to participate voluntarily. Face-to-face interviews were carried out under pandemic precautions, participants were informed about the study, and written informed consent was obtained.

Control Group

Participants in the control group completed baseline assessments including the Sociodemographic Characteristics Form, BBÜRDÖ, and the Pressure Injury Knowledge Test for Wheelchair Users via online forms administered simultaneously with telephone interviews. For participants with existing pressure injuries, home visits were conducted under pandemic precautions, and the Pressure Ulcer Scale for Healing (PUSH) was applied during baseline, follow-up, and post-test assessments.

After completion of the intervention group's training sessions, the control group was followed weekly for 12 weeks. During follow-up, the BBÜRDÖ and Pressure Injury Follow-up Form were administered via telephone interviews. No preventive pressure injury interventions were applied to the control group to avoid influencing knowledge outcomes. Routine counseling was not provided; participants were referred to healthcare services only upon request.

At the end of the 12-week follow-up period, post-test assessments were conducted using the BBÜRDÖ, Pressure Injury Knowledge Test for Wheelchair Users, and Pressure Injury Follow-up Form. Home visits were performed for participants with existing or newly developed pressure injuries, and the PUSH scale was applied. After completion of post-tests, educational sessions were offered to the control group.

Intervention Group

Baseline assessments in the intervention group included the Sociodemographic Characteristics Form, BBÜRDÖ, Pressure Injury Knowledge Test for Wheelchair Users, and Pressure Injury Follow-up Form, administered online with concurrent telephone interviews. Home visits were conducted for participants with existing pressure injuries, and the PUSH scale was applied.

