Participants attended structured educational sessions delivered online via Zoom. Four training groups (9–10 participants per group) completed three interactive sessions over two weeks. Each session lasted 60 minutes and covered pressure injury definition, etiology, risk factors, prevention strategies, and care practices. Educational materials were shared prior to the sessions, and a WhatsApp group was created to facilitate communication and interaction.

Following the training sessions, participants received weekly follow-up for 12 weeks with individualized counseling based on their needs. During follow-up, the BBÜRDÖ and Pressure Injury Follow-up Form were administered via telephone interviews. Participants who implemented at least one pressure injury prevention intervention were considered compliant. Home visits were conducted for participants with existing or newly developed pressure injuries, and the PUSH scale was applied.

Statistical Analysis

The study included 78 participants. Data were analyzed using IBM SPSS Statistics version 23. Descriptive statistics were used for categorical and numerical variables. Independent samples t-test and Mann–Whitney U test were used for between-group comparisons. Changes over time were analyzed using paired samples t-test, repeated measures analysis of variance, Cochran's Q test, and Wilcoxon test. Chi-square test was used for categorical comparisons. Statistical significance was set at $p < 0.05$.

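### BBÜRDÖ is collected at baseline and weekly for 12 weeks in both arms, but no baseline-adjusted, single-degree-of-freedom comparison between arms is named

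*Combined protocol and SAP*

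**What the plan says.** **Data collected.** The Control Group section places BBÜRDÖ at baseline ("Participants in the control group completed baseline assessments including the Sociodemographic Characteristics Form, BBÜRDÖ"), and the Intervention Group section does the same. After that, "the control group was followed weekly for 12 weeks", and in the intervention arm "participants received weekly follow-up for 12 weeks with individualized counseling based on their needs". Both sections say BBÜRDÖ was given by telephone during this follow-up. The Control Group section also describes a BBÜRDÖ post-test at the end of the 12 weeks, without saying whether this is the week-12 call or a further occasion.

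**Analysis named.** The Statistical Analysis section gives the between-arm tests in one sentence: "Independent samples t-test and Mann–Whitney U test were used for between-group comparisons". The next sentence begins "Changes over time were analyzed using paired samples t-test, repeated measures analysis of variance" and adds Cochran's Q and Wilcoxon tests.

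**Not stated.** The section does not link any test to BBÜRDÖ or say which occasion a t-test uses. It does not say whether the repeated measures ANOVA has an arm factor, or which of its effects would be read as the result. It names no primary outcome, covariate, summary measure or planned contrast.

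**The concern.** The trial has a baseline and about 12 follow-up scores per person. Two features of such data cheaply sharpen a comparison between arms. The baseline score explains part of the variation between people, and averaging several follow-up scores removes part of the week-to-week variation within a person. The two tests assigned to between-arm comparison use neither feature unless they are applied to a derived score, and the section describes none.

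Repeated measures ANOVA does not clearly fill the gap. Without an arm factor it gives no comparison between arms. With one, its arm-by-time test spreads the signal over as many degrees of freedom as there are follow-up occasions and does not reduce to one difference with a confidence interval. Its arm main effect is a single-degree-of-freedom test, but it averages the pre-training baseline into the outcome and does not adjust for baseline.

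At stake is a real difference in BBÜRDÖ being reported as non-significant when the data in hand could show it, and a report with several p-values but no adjusted estimate of how far the arms differ.

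**Working it through.** The documents give no sample size calculation, so there is no stated figure to reproduce.

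**Inputs from the documents**
- Total: "The study included 78 participants".
- Intervention arm: "Four training groups (9–10 participants per group) completed three interactive sessions over two weeks", which implies 4 × 9 = 36 to 4 × 10 = 40 people.
- Significance level: 0.05.
- Occasions: 1 baseline + 12 weekly calls = 13, hence 12 df for time (14 and 13 if the control arm's post-test is separate). These df follow from the visit count; the documents do not state them.

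**Assumptions**
- 39 per arm, two-sided test, complete data, independent participants, no systematic baseline difference between arms.
- BBÜRDÖ treated as a continuous score with SD 1 at every occasion.
- Equal correlation ρ = 0.7 between any two occasions.
- Effect d = 0.3 SD, constant over weeks 1–12.

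**Formulas.** For a one-df comparison the noncentrality is λ = (n/2) × effect² / v, where v is the variance of the score compared. Here n/2 = 19.5 and 19.5 × 0.3² = 1.755. Power comes from the noncentral F distribution on 1 and 76 df (75 for ANCOVA).

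| Comparison | v | λ | Power |
|---|---|---|---|
| t-test at week 12 | 1 | 1.755 | 0.26 |
| t-test on change to week 12 | 2(1 − 0.7) = 0.60 | 2.925 | 0.39 |
| ANCOVA at week 12 | 1 − 0.7² = 0.51 | 3.44 | 0.45 |
| ANCOVA on mean of weeks 1–12 | (1 + 11 × 0.7)/12 − 0.7² = 0.725 − 0.49 = 0.235 | 7.47 | 0.77 |

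The arm-by-time F test has λ = 19.5 × 0.3² × (12/13)/(1 − 0.7) = 5.4 on 12 and 912 df, giving power 0.26. The same λ on one df (12-week mean minus baseline) gives 0.63, so the fall from 0.63 to 0.26 is the cost of the 12 df.

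The ANOVA arm main effect over 13 occasions has a diluted effect of 0.3 × 12/13 = 0.277 and variance (1 + 12 × 0.7)/13 = 0.723. So λ = 19.5 × 0.277²/0.723 = 2.07 and power is 0.29.

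**Sources of the gain.** At week 12, baseline adjustment alone takes power from 0.26 to 0.45. Averaging then takes it from 0.45 to 0.77, a variance reduction of 0.51/0.235 = 2.2-fold. For ρ from 0.5 to 0.9 that reduction runs from 2.6- to 1.9-fold. With correlation that decays over time (0.85 to 0.95 per week), ANCOVA has power 0.26–0.34 at week 12 and 0.53–0.67 on the mean.

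**Sensitivity to effect size and correlation (constant effect)**

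| d, ρ | Week-12 t | Change t | Arm-by-time F | ANCOVA week 12 | ANCOVA mean |
|---|---|---|---|---|---|
| 0.3, 0.7 | 0.26 | 0.39 | 0.26 | 0.45 | 0.77 |
| 0.3, 0.9 | 0.26 | 0.83 | 0.76 | 0.85 | 0.99 |
| 0.5, 0.5 | 0.59 | 0.59 | 0.45 | 0.71 | 0.98 |
| 0.5, 0.7 | 0.59 | 0.80 | 0.72 | 0.86 | 0.99 |

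**Sensitivity to effect shape (d = 0.3, ρ = 0.7).** If the effect builds linearly to 0.3 SD at week 12, the average effect is 0.3 × 6.5/12 = 0.1625. For ANCOVA on the mean, λ = 19.5 × 0.1625²/0.235 = 2.19 and power is 0.31. That is below week-12 ANCOVA (0.45) and the arm-by-time F test (0.37). If the effect instead rises and levels off at week 2, 4, 6 or 8, the mean gives 0.73, 0.66, 0.57 or 0.48, still above 0.45.

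**The case against.** The strongest reply is that much of the criticised analysis is inferred. The section does not say that BBÜRDÖ is compared at one occasion, does not mention an arm-by-time test, and lists repeated measures ANOVA under change over time rather than under comparison of arms. The listed t-test could have been applied to a 12-week mean, or to that mean minus baseline (0.63 in the scenario above). This stands: the documents show a gap in specification, not a demonstrated choice of weak tests, so the loss has to be stated conditionally.

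A reader might infer three stronger claims, none of which the documents support.

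- *That every listed test wastes the weekly series.* A repeated measures ANOVA with an arm factor also yields a one-df main effect over all occasions. It is diluted by the baseline (0.29 at d = 0.3, ρ = 0.7), but it does use the series.
- *That the listed analysis would usually miss a lasting moderate effect.* At d = 0.5, ρ = 0.7, the week-12 t-test, change t-test and arm-by-time test have power 0.59 to 0.80. At d = 0.3, ρ = 0.9, the change t-test reaches 0.83 and the arm-by-time test 0.76. No effect size, SD or correlation is given that would select one scenario.
- *That a constant difference from week 1 is the natural expectation, so the 12-week mean must be the main result.* Training does end before the weekly calls, but individualized counseling in the intervention arm continues through all 12 weeks while controls receive no routine counseling. An effect that grows is therefore plausible, and in that case the mean is the weaker choice.

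It is also fair to say that BBÜRDÖ is not named as primary and its scale is not defined, and that an analysis introduced after the data were analyzed is open to the charge of being chosen for its result. Both points limit how the new result may be presented. Neither favors leaving out the baseline adjustment.

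**Conclusion.** The point holds in a limited form. Baseline and weekly BBÜRDÖ scores exist in both arms, the tests named for comparing arms are unadjusted, and no baseline-adjusted one-df contrast is named. In every constant-effect scenario tabulated, ANCOVA at week 12 is at least as powerful as the t-test at week 12, the change score and the omnibus test. In the reference case it gives 0.45 against 0.26, 0.39 and 0.26. The further step to 0.77 from averaging depends on a sustained effect and reverses under a linear build-up.

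These sizes illustrate the loss under assumed arm sizes, effect, correlation and complete data; they do not measure what this trial lost. The baseline adjustment can be recommended without settling the shape of the effect. The choice between week 12 and the 12-week mean is a choice of question, and the authors have to make and justify it.

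**What to change.** Add a short paragraph to the Statistical Analysis section that does the following.

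1. Compare arms on BBÜRDÖ by ANCOVA with baseline BBÜRDÖ as covariate, and report the adjusted difference with its 95% CI.
2. Report it at week 12 and for each participant's mean over weeks 1–12. State which is the main result and why: the mean suits a sustained effect, week 12 an effect still building as counseling continues.
3. Say whether the control arm's post-test is the week-12 call, and how missed calls are handled in the mean. If scores trend over time, an average of whichever calls were completed compares different mixes of weeks.
4. Say whether the repeated measures ANOVA includes an arm factor, and which of its effects, if any, is used to compare arms.
5. Label the analysis post hoc unless it was specified before the data were seen, because the section reports the analysis in the past tense.

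The cost is one paragraph and a short re-run on data already collected, with no new measurements. The limits are the post hoc label and the need to defend one of two summaries that can give different answers.

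### If run on the weekly series, repeated measures ANOVA and Cochran's Q would drop anyone with one missed call and, without a sphericity correction, reject too often

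*Combined protocol and SAP*

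**What the plan says.** Both arms had the same weekly schedule. In the Control Group section, "the control group was followed weekly for 12 weeks". In the Intervention Group section, "participants received weekly follow-up for 12 weeks with individualized counseling based on their needs". The same sentence on weekly instruments appears in both sections: "During follow-up, the BBÜRDÖ and Pressure Injury Follow-up Form were administered via telephone interviews".

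BBÜRDÖ was also given at baseline in both arms. The Pressure Injury Follow-up Form is listed at baseline for the intervention arm only. The control list reads: "Participants in the control group completed baseline assessments including the Sociodemographic Characteristics Form, BBÜRDÖ, and the Pressure Injury Knowledge Test for Wheelchair Users". The control arm has a described post-test at the end of the 12 weeks that includes both instruments.

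The Statistical Analysis section gives between-group comparisons to the independent samples t-test and the Mann–Whitney U test. Changes over time are given to the paired t-test, "repeated measures analysis of variance", Cochran's Q and the Wilcoxon test. It does not say which outcome or which weeks enter each test, how missed calls were handled, or whether a sphericity test or correction was used. On sample size it says only: "The study included 78 participants".

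**The concern.** The paired t-test and Wilcoxon test compare two occasions. For three or more, the section offers only repeated measures ANOVA and Cochran's Q, and the weekly BBÜRDÖ and Follow-up Form are the natural data for them. Two separate weaknesses follow if they are used that way.

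- **Complete rows.** In their classical form both tests use only participants observed on every occasion entered. One missed call discards all of a participant's other weeks. With 12 calls each, a low miss rate per call can remove many people. Those left are the easiest to reach. Intervention calls carried individualised counselling and control calls did not, so reasons for answering may differ by arm.
- **Sphericity.** Repeated measures ANOVA assumes that differences between any two occasions have equal variance. Weekly scores usually correlate more between adjacent weeks than between distant ones, which breaks this assumption. The uncorrected F-test then rejects too often. Cochran's Q rests on a related condition.

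Curing one does not cure the other: a sphericity correction does not bring back dropped participants, and complete data do not restore sphericity.

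**Working it through.** The plan states no power, dropout or missing-data figure, so there is nothing of its own to reproduce.

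**Inputs from the document.** Total 78 (Statistical Analysis); 12 weekly calls in each arm; four training groups of 9–10.

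**Assumptions.** Miss rate per occasion, week-to-week correlation, event rate for the binary outcome, BBÜRDÖ as a numerical score, and 39 per arm. The last fits the training groups: 4 × 9 = 36 to 4 × 10 = 40, and 78 / 2 = 39.

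**1. Occasions.**
- BBÜRDÖ: 1 baseline + 12 calls = 13, or 14 if the post-test is separate from the twelfth call.
- Follow-up Form: 12–13 in control (no baseline form listed) and 13–14 in intervention.

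**2. Participants with complete rows.** With independent misses at rate m over k occasions, the expected number is 78 × (1 − m)^k.

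| k | m = 2% | m = 5% | m = 10% |
|---|---|---|---|
| 12 | 78 × 0.785 = 61 | 78 × 0.540 = 42 | 78 × 0.282 = 22 |
| 13 | 78 × 0.769 = 60 | 78 × 0.513 = 40 | 78 × 0.254 = 20 |
| 14 | 78 × 0.754 = 59 | 78 × 0.488 = 38 | 78 × 0.229 = 18 |

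At m = 0 all 78 remain. Whether there were 12, 13 or 14 occasions makes little difference.

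**3. If misses cluster in the same people.** Under a beta-binomial model with within-person correlation r, let s = 1/r − 1 and b = (1 − m)s. The chance of no miss in 12 calls is the product over i = 0 to 11 of (b + i)/(s + i).
- m = 5%: r = 0.1 gives 0.668 × 78 = 52.1; r = 0.3 gives 0.788 × 78 = 61.5.
- m = 10%: r = 0.1 gives 0.440 × 78 = 34.3; r = 0.3 gives 0.618 × 78 = 48.2.

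The independent-miss figures are therefore towards the pessimistic end.

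**4. Type I error of the F-tests.** Null simulation at nominal 5%: 4,000 runs, AR(1) correlation ρ, 13 occasions, 39 in one arm for the time effect and 39 per arm for arm × time. Epsilon measures departure from sphericity (1 = none).

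| ρ | epsilon | time, uncorrected | time, Greenhouse-Geisser | arm × time, uncorrected | arm × time, Greenhouse-Geisser |
|---|---|---|---|---|---|
| 0.5 | 0.67 | 7.6% | 3.8% | 8.7% | 4.8% |
| 0.7 | 0.45 | 10.8% | 4.8% | 10.3% | 4.9% |
| 0.9 | 0.27 | 13.5% | 4.4% | 12.9% | 4.9% |

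With 14 occasions the uncorrected rates run from 7.3% to 13.6% across both tests.

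**5. Cochran's Q.** Same set-up within one arm of 39, 13 occasions, event rates 0.2 and 0.5, chi-square reference: 5.4%–6.3% at ρ = 0.5, 6.9%–8.3% at 0.7, and 8.8%–9.2% at 0.9.

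**The case against.** The strongest reply is that nothing in the document puts all the weekly points into these tests; a few selected time points may have been used. That stands, and the point is conditional on it. Using the weekly series is an inference from the schedule and from the list of tests.

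Second, between-arm comparisons are assigned to the t-test and Mann–Whitney test, and no arm × time test is named. At a single time point those tests need only that time point, so a missed weekly call costs nobody and sphericity plays no part. This stands for the arm comparison. It does not remove the sphericity problem, because the within-arm time effect, which the plan does list, inflates by a similar amount.

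Third, no missed calls are reported and no correction is ruled out. With complete data the sample loss is zero, and with Greenhouse-Geisser degrees of freedom the simulated error is about 5% or less. Both stand; the document leaves both open.

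A reader might infer that participants were in fact lost, that the arm comparison is biased, or that the reported p-values are too small. The document supports none of these. It gives no count of missed calls by arm, complete-case bias depends on why calls were missed, and the absence of a stated correction does not show that none was applied. Nor can 13 occasions be taken for granted for Cochran's Q, since the control arm has no listed baseline Follow-up Form.

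**Conclusion.** The concern holds in conditional form. The only listed methods for three or more occasions suit a long weekly series poorly, and the plan is silent on the two facts that decide whether harm occurred: missed calls and sphericity correction.

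If the weekly series was analysed this way, the sample loss ranges from none to most of the 78. Without a correction, the F-tests for change would run at roughly one and a half to nearly three times the nominal 5%, and Cochran's Q at up to about twice. The miss rates, clustering, AR(1) correlations, event rates and even split behind these figures are assumptions. Attrition bias is a risk and is not shown. Confidence is high in the criticism of the method and moderate at most in any realised harm. The plan should be changed, but the listed single-time-point arm comparisons do not fall with this point.

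**What to change.** - **Weekly BBÜRDÖ:** fit a linear mixed model by REML to all available weeks after baseline, with arm, week, arm × week and baseline BBÜRDÖ. State a serial covariance structure, such as AR(1), and check it against an unstructured or participant-effect alternative.
- **Weekly injury status:** use logistic GEE or a mixed logistic model. Unlike Cochran's Q, either can compare the arms over time.
- **Population:** keep every participant in the assigned arm.
- **Status:** the section is written in the past tense. If the original analysis is already done, label these models post hoc and report them beside it.
- **Minimum, if the listed tests are kept:** say which outcomes and weeks entered each test, apply Greenhouse-Geisser degrees of freedom to any repeated measures ANOVA, and report missed calls and analysed numbers per arm.

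The cost is revised wording and a re-run in the same statistical package, with no new data. The small downside is reliance on further assumptions: the mixed models need data missing at random, ordinary GEE needs a stronger condition unless weighted, and a covariance structure has to be chosen. The minimum step costs a few sentences and a table of counts.

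### No primary outcome or multiplicity control is stated; testing each of four outcomes once at p < 0.05 gives about a 9% to 18.5% chance of at least one false positive

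*Combined protocol and SAP*

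**What the plan says.** The Statistical Analysis section gives tests by type, not by outcome:

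- Between groups: "Independent samples t-test and Mann–Whitney U test were used for between-group comparisons".
- Over time: "Changes over time were analyzed using paired samples t-test, repeated measures analysis of variance, Cochran's Q test, and Wilcoxon test".
- Categorical data: "Chi-square test was used for categorical comparisons".
- Threshold for all of these: "Statistical significance was set at" p < 0.05.

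The outcomes have to be read from the Control Group and Intervention Group sections. At the end of follow-up in the control group, "post-test assessments were conducted using the BBÜRDÖ, Pressure Injury Knowledge Test for Wheelchair Users, and Pressure Injury Follow-up Form". PUSH is added for participants who have a pressure injury. For the 12 weeks of weekly contact, both group sections say the same: "During follow-up, the BBÜRDÖ and Pressure Injury Follow-up Form were administered via telephone interviews". The Knowledge Test is not listed for those calls.

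The only hint of a leading outcome is the reason given for withholding prevention from controls: "No preventive pressure injury interventions were applied to the control group to avoid influencing knowledge outcomes". Nothing in the Statistical Analysis section follows that up.

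**The concern.** A threshold of 0.05 limits the error of a single test. When several outcomes are each tested at that level and none is named in advance as the one that decides, the intervention can be called effective on whichever outcome crosses the line. The error rate of that overall claim is then above 5%. A reader of the results also cannot tell which comparison was the planned test and which was picked out afterwards. The weekly contacts and the list of within-group tests leave room for more comparisons, so the size of the problem depends on choices the document does not record.

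**Working it through.** **Inputs from the document**

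- Threshold per test: 0.05 (Statistical Analysis). Sidedness is not stated.
- Outcome measures: Knowledge Test, BBÜRDÖ, Follow-up Form and PUSH (Control Group, Intervention Group).
- PUSH: only participants with an existing or new injury.
- Weekly instruments by telephone: BBÜRDÖ and Follow-up Form, over 12 weeks.
- Total sample: 78.

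**Assumptions, not in the document**

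- Two-sided tests and no true effect on any outcome.
- The Follow-up Form yields one outcome, injury occurrence.
- One between-group test per outcome. Compliance is left out because it is defined only in the Intervention Group section.
- Correlations between outcomes are unknown, so a range is shown.
- Equal groups of 39 (78/2) for the weekly calculation.

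**Step 1. The stated level.** For one test, 1 − 0.95 = 0.05. The stated 5% is an overall error rate only if a single test is made.

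**Step 2. Four independent tests.** 1 − 0.95^4 = 1 − 0.8145 = 0.1855, or 18.5%. That is 3.7 times 5%.

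**Step 3. Three full-sample tests, without PUSH.** 1 − 0.95^3 = 1 − 0.8574 = 0.1426, or 14%.

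**Step 4. Correlated outcomes.** Simulated two-sided z-tests with the same correlation between every pair of outcomes:

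| Correlation | Four tests | Three tests |
|---|---|---|
| 0 | 18.5% | 14% |
| 0.3 | 17% | 14% |
| 0.5 | 16% | 13% |
| 0.7 | 13% | 11% |
| 0.9 | 9% | 8% |

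**Step 5. Weekly testing of BBÜRDÖ, conditional.** If the groups were compared by a separate t-test at each of the 12 weekly occasions, the chance of at least one p < 0.05 would be as follows (simulation, 20,000 runs, 39 per group, AR(1) correlation from week to week):

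| Week-to-week correlation | Any false positive in 12 weeks |
|---|---|
| 0.5 | 41% |
| 0.7 | 34% |
| 0.8 | 29% |
| 0.9 | 21% |

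Baseline is excluded, because a difference there is not an effect claim.

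**Step 6. After correction.** Bonferroni over four tests uses 0.05/4 = 0.0125 each. If independent, the overall rate is 1 − 0.9875^4 = 0.049, and it cannot exceed 5% under any correlation. Holm has the same guarantee. It compares the ordered p-values with 0.0125, 0.0167, 0.025 and 0.05, so it never rejects less than Bonferroni.

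**The case against.** Several points on the other side are sound.

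- **Weekly testing is not stated.** A reader might infer that four outcomes are each tested at 12 weekly time points, or 48 tests. The document does not support this. Only two instruments are listed for the weekly calls. Repeated measures analysis of variance and Cochran's Q can each cover all occasions in one test. The 21% to 41% range is what the wording leaves open, not what it specifies.
- **The document promises no familywise rate.** The 0.05 is a per-test level, so no stated figure is contradicted. What is missing is a rule that turns several per-test results into one claim.
- **18.5% is the upper end for four tests.** Correlation lowers it, and PUSH is not a full-sample test. With three tests and high correlation the figure is about 8%. This limits the size but does not bring it back to 5%.
- **A primary outcome may be fixed elsewhere.** The text says it was prepared for a registry entry, and no other record was examined here. The finding is about this document only.
- **Knowledge cannot simply be taken as primary.** It is tempting to infer this from the sentence on controls. That sentence explains a design choice in one group. Weekly collection of BBÜRDÖ and injury data could as easily point to those outcomes. Because the study is described as already analysed, choosing a primary now on that basis would be post hoc.

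The core remains: one threshold, several outcomes, no ranking and no adjustment.

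**Conclusion.** The concern holds in a limited form. With a single between-group test on each of four outcomes, the plan's rule gives an 18.5% chance of at least one false positive if the tests are independent, about 17% to 13% at correlation 0.3 to 0.7, and about 9% at 0.9. That is roughly two to nearly four times the per-test level. Dropping PUSH gives 14% if independent. These figures assume two-sided tests and no true effect on any outcome; within-group tests used as evidence of efficacy would add to them. The weekly figures of 21% to 41% apply only if the weeks are tested separately and rest on an assumed correlation structure, so they should not be quoted as a property of the plan. The data are not invalidated. The consequence is that an isolated p < 0.05 cannot be read as evidence at the 5% level for the overall claim that the intervention works.

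**What to change.** 1. **If a primary outcome was fixed before data were seen,** state it and where it is documented. Test its between-group difference at the end of the 12-week follow-up at 0.05, and apply Holm to the other outcomes. This holds the main claim at 5% and the secondary group of tests at 5%. The two together could reach 5% + 5% = 10% unless secondary claims are made only when the primary test is significant, so say which is intended.
2. **If no such outcome can be documented,** say so and apply Holm to the end-of-follow-up between-group tests of all four outcomes.
3. **In either case,** label PUSH as a comparison within the injured subset. That subset includes injuries that arose after the intervention, so it is not a comparison of the groups as formed.
4. **Intermediate weeks:** report estimates with 95% confidence intervals, or one omnibus test per outcome, with no week-by-week significance claims.

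The cost is a small reanalysis of data already collected plus revised text. Adjusted p-values become less favourable: Holm multiplies the smallest by four in the fallback, or by three if one of the four outcomes is a documented primary.
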